The purpose of this study is to determine whether topical capsaicin-induced sensitization has any influence on ventral horn activity. We hypothesize that capsaicin induces a change in individual motor unit activity, as well as the recruitment pattern of many motor units, and may affect motor unit activity at different segmental levels from the level of capsaicin application.

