2.3 Study Procedures for EMG Analyses

This section outlines the procedures for the EMG analysis. For the sEMG data, the pre-recording motor units will be matched with an algorithm implemented in MATLAB (Mathworks, version 2018a), described in section 2.3.1, in order to determine the aberration of recruitment pattern after treatment.

For the iEMG data, the pre- and post-recording motor units will also be matched using an algorithm implemented in MATLAB (Mathworks, version 2018a), described in 2.3.2. The variability of that motor unit shape will be compared before and after capsaicin and between groups.

2.3.1 *Surface EMG*

Recorded sEMGs will be analyzed in *Neuromap* [32], which provides an average template, average amplitude, and order of recruitment of each motor unit detected and isolated from the raw signal using *Delsys*' motor unit decomposition algorithm [33]. Each motor unit template will then be analyzed based on their “overall match” in shape and amplitude.

Shape Analysis

The motor unit signal that will be obtained from M electrode contacts at T consecutive time samples will be assembled into an $M \times T$ matrix. This matrix will then be compressed into a single vector to create a motor unit “signature” [34]. This will be done by taking the recordings from all electrode contacts at a single time step and concatenating it to the recordings from all contacts at the next time point. This concatenation will be repeated to the time T to create the signature (**Figure 1**). This process will be performed for the pre- and post-recording motor units for each participant.

The shape of each detected pre-recording motor unit will be compared to the shape of each post-recording motor unit via the cross-correlation function, *xcorr*, in *Matlab* (Mathworks, 2018a). This function returns a normalized value between 0 – 1 between each pre- and post-recording motor unit. Cross-correlation values between pre- and post-recording motor unit pairs that are

below a preset threshold of 0.8 [35] will be set to 0 as the pair is unlikely to be from the same motor unit.

Amplitude Analysis

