The motor unit average amplitudes obtained from the *Neuromap* software will be used for calculating an amplitude ratio between pre- and post-recording motor units. This amplitude ratio will be calculated for each pre/post motor unit pair to determine similarities in the amplitude. Similar to the shape analysis, amplitude ratios that are below a preset threshold of 0.8 or above 1.2 are set to 0. This ratio will be normalized to be within a scale from 0 – 1 to allow for comparison between shape and amplitude using the following equation (Eq.1) when the amplitude ratio is above one.

$$\text{Normalized Amp. Ratio} = 1 - \text{Amp. Ratio} \quad (1)$$

The numbers from the shape analysis and amplitude analysis, which are not set to 0, will be averaged together to express an “overall match” between pre- and post- motor units from each participant. As mentioned, based on Henneman’s size principle, motor units should be recruited in the same order with smaller units being recruited first and subsequent motor units are recruited as more force is needed [19]. To observe whether this principle is upheld or violated, the reorganization of the recruitment will be identified by how much earlier or later the similar motor units were recruited. In order to quantify the recruitment, the difference in the order of recruitment between the pre and post recording will be calculated. Recruitment order of motor units will be

determined through a custom automated search algorithm (Algorithm 1), which will determine the best match between pre- and post-recording motor units.

Algorithm 1: Automated Motor Unit Matching method

Input: Matrix of averaged values from shape and amplitude analysis

Output: Matched pre-post motor units

- 1: **loop** through each pre-motor unit (row) and each post-motor unit (col)
- 2: **if** value at current location is the highest in that row and column, **and** the number is not equal to zero
- 3: **Record** match between the pre- and post- motor unit, and set the row and col to 0 (i.e. remove the pre- and post- motor unit from further pairing)
- 4: Return matched pre-post motor unit pairs

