The average recruitment order difference for each motor unit will be obtained for each participant. Following this, for each participant, the recruitment difference for all of their motor units will be averaged, to obtain one vector of average recruitment changes per person. This final matrix containing numbers on a continuous scale, will be used for statistical testing. See Appendix A for a detailed explanation of the matrix set up.

2.3.2 *Intramuscular EMG analysis using template matching*

Recorded iEMGs will be thresholded using the median absolute deviation estimate approach (**Eq.2**) to find the peak location of motor unit action potentials (MUAPs) [36].

$$Threshold = 10 \times \frac{Median(|X|)}{0.6745} \quad (2)$$

Each detected peak, along with 12.5 ms before and after will be stored and used for analyses. These detected MUAPs will then be clustered to determine the number of motor units present in the recording. In particular, the first detected peak and its surrounding environment (i.e. the MUAP) forms the first motor unit template. Subsequent detected MUAPs will be compared to the first template using cross correlation. If the cross correlation is more than 0.85, it will be determined as the same MUAP and added to that motor unit cluster and the template will be updated. However, if the cross-correlation is less than 0.85, it will be classified as a different motor unit and a new template cluster will be created for comparison.

This process will be repeated until all of the detected MUAPs in the pre- and post-recording are classified. The MUAP cluster with the highest number of MUAPs, for the pre-recording, will be compared with all MUAP clusters found in the post-recording for each participant. The MUAP cluster in the post that has the highest cross-correlation value will be considered “matched.” Participants that do not have matched MUAPs with cross-correlation values above or equal to 0.95 will not be used for statistical analysis.

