2.4 Statistical Methods

2.4.1 Surface EMG

An independent samples t-test will be performed on the difference in recruitment position using treatment as the factor for the trapezius muscle. In particular, the statistical test will compare

post-pre capsaicin recruitment differences against post-pre placebo recruitment differences. The average difference in recruitment order will be used to avoid bias of having multiple data points per participant that correspond to different motor units.

2.4.2 *Intramuscular EMG*

From the intramuscular EMG algorithm mentioned in section 2.3.2, the resultant matrices will be the variances for the pre-recording motor unit trains. The statistical model used will assess the difference between the pre- and post- recording motor units for each capsaicin and placebo as well as a between group comparison (Post-Pre capsaicin motor unit variance vs. Post-Pre placebo motor unit variance). These analyses would provide insight into our hypothesis that sensitization induced by capsaicin effects upon the motor unit characteristics. Either an independent samples t-test or a Kruskal-Wallis H test will be performed, depending on how many participants' pre and post motor units match up.

3 Sample Size Calculation

The minimum sample size required per group to detect whether a significant difference exists between two means for one dependent variable was calculated with a confidence level of 95%, a 80% statistical power level and 5% error. A mean detectable difference of 5 for the dependent variable, mean motor unit recruitment change, and an estimated standard deviation of 3 was used. The estimated sample size was 7 people per group; however, considering a 20% drop out rate, the suggested sample size was 9 people per group. This analysis was completed using PASS Software, version 15.

4 Conclusions

This may provide some insights for the neurophysiological influence of central sensitization on changes in efferent responses and movement patterns that occur in patients with persistent pain. However, the clinical implication of this experimental findings on the movement properties needs to be further investigated.

5 References

- [1] IASP, "Classification of chronic pain: descriptions of chronic pain syndromes and definitions of pain terms," *Pain* 1994; Suppl 3: 1–226.
- [2] I. o. Medicine, Relieving Pain in America: A Blueprint for Transforming Prevention, Care, Education, and Research, Washington,DC: The National Academies Press, 2011.

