APPENDIX A

MUPRE	MUPOST	Difference Array
1	9	8
2	8	6
4	13	9
5	16	11
6	15	9
8	19	11
14	18	4

Average Difference per person (for T test USE):

$= \text{Average}(\text{Differences})_{\text{per person}}$

$$= \frac{(8) + (6) + (9) + (11) + (9) + (11) + (4)}{7}$$

$$= 8.286$$

Supplementary Figure 1: Pre/Post Difference

In order to compare the reorganization in recruitment, the difference in order of recruitment was calculated and put into an array. This difference array was calculated for each person, and an average difference in recruitment per person was analysed using a t-test. The reason for having an average per person was to avoid any bias by having multiple data points per person that correspond to different motor units. Assumptions of normality and homogeneity of variances were verified from the Shapiro- Wilk test ($p=0.187$) and Levenes Statistic($p=0.081$), therefore a t-test can be used.

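### The averaged post-minus-pre recruitment position cannot show whether matched motor units changed order, and it moves with which unmatched units were detected

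*Combined protocol and SAP*

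**What the plan says.** The hypothesis at the end of the Introduction is that capsaicin changes individual motor unit activity "as well as the recruitment pattern of many motor units". Section 2.3.1 ties the surface EMG measure to Henneman's size principle: "To observe whether this principle is upheld or violated, the reorganization of the recruitment will be identified by how much earlier or later" similar units were recruited.

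The measure is built in four steps:

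- The Neuromap software supplies the "order of recruitment of each motor unit detected and isolated from the raw signal", so a position is counted among all units found in that recording.
- Pre and post units are paired, using a shape threshold of 0.8 and an amplitude-ratio window of 0.8 to 1.2.
- The position differences of the paired units are reduced to one value per participant: "for each participant, the recruitment difference for all of their motor units will be averaged".
- Section 2.4.1 applies an independent t-test to "post-pre capsaicin recruitment differences against post-pre placebo recruitment differences".

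Appendix A gives a worked example with seven matched units and a value of 8.286, described this way: "In order to compare the reorganization in recruitment, the difference in order of recruitment was calculated and put into an array". Section 3 sizes the study on the same variable: "A mean detectable difference of 5 for the dependent variable, mean motor unit recruitment change", with SD 3.

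**The concern.** The size principle is a statement about order. A mean of differences depends only on the two means, so the pairing of units with positions, which is where order information lies, drops out. If so, a null result would not show that order was preserved, and a significant result would not show that it was disturbed.

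Positions are also counted among all detected units, while differences are averaged over matched units only. A unit can be unmatched for three reasons: it was newly recruited, it was missed in the other recording, or it failed the matching thresholds. The plan does not separate these causes, does not re-rank the matched units, and does not account for the numbers detected or matched. This is the only test described for the surface EMG data and the variable that sets the sample size.

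**Working it through.** **Plan's own figures.** Section 3 uses "confidence level of 95%, a 80% statistical power level and 5% error", difference 5, SD 3. Sidedness is not stated; two-sided is assumed because it reproduces the plan. With effect size 5/3, the two-sample t calculation gives n = 6.76, so 7 per group (power 81.6%). Then 7/(1 − 0.2) = 8.75, so 9. Both agree with the plan. Appendix A also reproduces: (98 − 40)/7 = 58/7 = 8.286.

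**Inputs from Appendix A.** Pre positions 1, 2, 4, 5, 6, 8, 14 (sum 40). Post positions of the same units 9, 8, 13, 16, 15, 19, 18 (sum 98).

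**Step 1: order cancels.** For m matched units, mean(post − pre) = mean(post) − mean(pre). Every assignment of the seven post positions to the seven units gives 8.286: all 7! = 5,040 were computed. Sorted order (tau 1) and full reversal (tau −1) are among them. The actual re-ranked post order is 2, 1, 3, 5, 4, 7, 6. Of 21 pairs, 18 keep their order, so tau = (18 − 3)/21 = 0.714. Matched order is largely preserved while the endpoint exceeds the planned difference of 5.

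**Step 2: what remains.** A matched unit's position is its rank among matched units plus the number of unmatched units ahead of it. The ranks average (m + 1)/2 in both recordings and cancel. The endpoint is therefore the mean number of unmatched units ahead, post minus pre:

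- Pre: (40 − 28)/7 = 1.714
- Post: (98 − 28)/7 = 10.000
- Difference: 8.286

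**Step 3: sensitivity to detection.** Unmatched units hold post positions 1 to 7. Had they not been detected, the post positions would be 2, 1, 6, 9, 8, 12, 11 (sum 49). The endpoint would be (49 − 40)/7 = 1.286, with tau still 0.714. Each extra unmatched post unit ahead of all matched units adds exactly 1.0.

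**Step 4: absolute differences, if meant.** Over the 5,040 re-pairings the mean absolute raw difference runs from 8.286 to 10.0, so order has some influence. Removing the same seven units gives (1 + 1 + 2 + 4 + 2 + 4 + 3)/7 = 17/7 = 2.43. The dependence on detection remains.

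**Step 5: illustration on assumed inputs.** Assumptions: 10 per arm, N = 20 or 30 underlying units, 40% or 60% detected, order noise SD 1 in controls and N/4 under moderate re-ordering, 400 trials per setting. Rejection rates over the four settings:

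| Scenario under capsaicin | Planned (signed) test | Test on tau |
|---|---|---|
| (a) Moderate re-ordering | 4.5–5.8% | 40–100% |
| (b) No order effect, post detection a quarter lower | 15–52% | 1–7% |
| (c) Similar expected yield, 5 late units replaced by 5 new early ones | 39–92% | 1–5% |

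A repeat of the planned test in (a) and (b) gave 2–5% and 17–52%. Scenarios (b) and (c) cannot be told apart from the planned value alone. The tau rates at the sparsest setting should be read loosely: expected matches there are 20 × 0.4 × 0.4 = 3.2.

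A separate run (30 units, 60% detected, perfect matching, 9 per group, 600 trials) rejected 5.2% with capsaicin order scrambled, 5.5% with it reversed and 5.5% with no effect. With order kept and capsaicin post detection at 70%, 80% or 90%, it rejected 26%, 79% and 99%.

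**The case against.** **The plan never says signed.** Every Appendix A difference is positive, so the table does not exclude absolute values. On that reading the endpoint would carry order information. With all seven units matched, full reversal would give 24/7 = 3.43 against 0 for preserved order, and a run of scenario (a) with absolute differences (300 trials) rejected in about 12–71%. This stands as a reason to state the convention. It does not rescue the endpoint: the directional wording of sections 2.3.1 and 2.4.1 points to signed differences, and step 4 shows that detection still drives the absolute version.

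**A shift against all detected units is also a change in recruitment.** If the seven early post units in Appendix A were truly newly recruited, that is part of the stated hypothesis, and scenario (c) shows that tau would miss it. This stands, and is why the shift should be kept. The planned value still cannot distinguish new recruitment from missed or rejected units.

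**The placebo arm controls for detection.** It does so only for changes common to both arms. The documents give no size or direction for any difference between arms.

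**Five units is a worst case.** It requires the extra units to lie ahead of all matched ones, and an average excess of five per participant in one arm. An extra unit at a random position adds about 0.5: in the separate run, 9 more detected units (60% to 90% of 30) moved the mean by 4.5. This stands as a limit on the likely size.

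**Tau measures stability of order, not order by size.** It would equal 1 if both recordings broke the size rule identically. This stands.

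**Appendix A reads as if the analysis had been run**, since it reports normality and variance test results. If so, a new primary measure would be a post hoc choice and should be labelled as one.

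**Conclusion.** The concern holds and must be fixed. On the signed reading it is an identity: the endpoint has no information on order among matched units, so the t-test cannot show whether the size principle is upheld or violated among them. A null result does not mean order was preserved, and a significant one cannot be read as re-ordering. A significant result may be a true net shift or an arm difference in which units were detected or matched.

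The exact results are the invariance at 8.286, the fall to 1.286 (2.43 if absolute) when seven unmatched units are removed, and 1.0 per unmatched unit ahead of all matched ones. They rest only on Appendix A and on positions being counted among all detected units. The rejection rates rest on assumed detection rates and order noise and are illustrative. The sample size arithmetic is correct; the fault lies in the variable it was applied to.

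**What to change.** Define two measures per participant and name one as primary.

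1. **Order.** Re-rank the matched units 1 to m within each recording. Compare arms on Kendall's tau, or on mean absolute re-ranked displacement scaled by m. State a minimum m in advance and list participants below it by arm.
2. **Net shift.** Keep the raw-position mean, state that it is signed, and test it as a separate measure of earlier or later recruitment. Report it with, or adjust it for, the numbers of detected and matched units per recording and arm.

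Restate the planning assumption (5, SD 3) on the scale of the order measure. The documents give no expected difference or SD on that scale, so a sample size for it cannot be derived from them. If the size element is to be tested as well, the unit amplitudes that section 2.3.1 says are available would have to enter the analysis.

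The cost is SAP wording and a few lines of MATLAB, with no new data or participants. There are three downsides:

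- Tau is undefined below two matches and imprecise with few. Its SD under random order, √[2(2m + 5)/(9m(m − 1))], is 0.64 at m = 3, 0.41 at m = 5, 0.32 at m = 7 and 0.25 at m = 10.
- A minimum m may exclude participants, possibly more in one arm if detection differs. At 20 units and 40% detection about 15% would have fewer than two matches, against about 29% with post detection a quarter lower.
- Two tested measures need a stated primary.

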2.4 Statistical Methods

2.4.1 Surface EMG

An independent samples t-test will be performed on the difference in recruitment position using treatment as the factor for the trapezius muscle. In particular, the statistical test will compare

post-pre capsaicin recruitment differences against post-pre placebo recruitment differences. The average difference in recruitment order will be used to avoid bias of having multiple data points per participant that correspond to different motor units.

2.4.2 *Intramuscular EMG*

From the intramuscular EMG algorithm mentioned in section 2.3.2, the resultant matrices will be the variances for the pre-recording motor unit trains. The statistical model used will assess the difference between the pre- and post- recording motor units for each capsaicin and placebo as well as a between group comparison (Post-Pre capsaicin motor unit variance vs. Post-Pre placebo motor unit variance). These analyses would provide insight into our hypothesis that sensitization induced by capsaicin effects upon the motor unit characteristics. Either an independent samples t-test or a Kruskal-Wallis H test will be performed, depending on how many participants' pre and post motor units match up.

3 Sample Size Calculation

The minimum sample size required per group to detect whether a significant difference exists between two means for one dependent variable was calculated with a confidence level of 95%, a 80% statistical power level and 5% error. A mean detectable difference of 5 for the dependent variable, mean motor unit recruitment change, and an estimated standard deviation of 3 was used. The estimated sample size was 7 people per group; however, considering a 20% drop out rate, the suggested sample size was 9 people per group. This analysis was completed using PASS Software, version 15.

4 Conclusions

This may provide some insights for the neurophysiological influence of central sensitization on changes in efferent responses and movement patterns that occur in patients with persistent pain. However, the clinical implication of this experimental findings on the movement properties needs to be further investigated.

5 References

- [1] IASP, "Classification of chronic pain: descriptions of chronic pain syndromes and definitions of pain terms," *Pain* 1994; Suppl 3: 1–226.
- [2] I. o. Medicine, Relieving Pain in America: A Blueprint for Transforming Prevention, Care, Education, and Research, Washington,DC: The National Academies Press, 2011.

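### No primary outcome is named: Section 3 plans its 5% error for one variable, but Section 2.4 ties iEMG tests, two of them within-arm, to the same hypothesis

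*Combined protocol and SAP*

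**What the plan says.** Section 3 (Sample Size Calculation) sets the size needed to "detect whether a significant difference exists between two means for one dependent variable", with a "confidence level of 95%, a 80% statistical power level and 5% error". It attaches these to a single variable: "A mean detectable difference of 5 for the dependent variable, mean motor unit recruitment change", where "an estimated standard deviation of 3 was used". The result is 7 per group, or 9 after allowing for 20% dropout.

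Section 2.4 plans four comparisons:

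1. Section 2.4.1: between-arm t-test on the post-minus-pre change in sEMG recruitment order, trapezius.
2. Section 2.4.2: between-arm comparison of the post-minus-pre change in iEMG motor unit variance.
3. Section 2.4.2: pre versus post iEMG within capsaicin.
4. Section 2.4.2: pre versus post iEMG within placebo.

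Section 2.4.2 then says of the iEMG set: "These analyses would provide insight into our hypothesis that sensitization induced by capsaicin effects upon the motor unit characteristics". The hypothesis at the end of the Introduction joins both outcomes without ranking them: "capsaicin induces a change in individual motor unit activity, as well as the recruitment pattern of many motor units". Nowhere do the documents label an outcome primary, secondary or exploratory. They give no testing order and no multiplicity rule, and Section 2.4 states no significance level.

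**The concern.** There are two separate problems.

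**Several routes to the same claim.** The error rate was planned for one variable, but four results are open to being read as evidence for one hypothesis. Without a stated primary outcome, nothing in the plan prevents an isolated iEMG result from carrying the conclusion when the sEMG test is null. The chance of a false claim over the set is then above 5%.

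**Within-arm comparisons.** In a randomised, placebo-controlled study only the between-arm contrast isolates capsaicin. The second recording follows a one-minute repeated shoulder task, a first needle recording and a twenty-minute wait (Sections 2.2.1 and 2.2.2). Any effect of time, repetition or needle position that is common to both arms enters each pre-post comparison. A significant change under capsaicin with a non-significant one under placebo can therefore arise with no difference between arms.

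**Working it through.** **Step 1. Reproduce Section 3.**
Inputs from Section 3: difference 5, SD 3, error 0.05, power 0.80. Assumed: two-sided and 1:1, neither of which is stated. Two-sample t-test with the noncentral t distribution:

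- noncentrality = 5 / (3 × √(2/n)), with 2n − 2 degrees of freedom
- n = 6: noncentrality 2.887, power 74.0%
- n = 7: noncentrality 3.118, power 81.6%

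So 7 per group is reproduced (a one-sided test would need only 6). Dropout: 7 / 0.8 = 8.75, rounded up to 9, also reproduced. For this one test the stated 5% error and 80% power hold.

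**Step 2. Chance of at least one false positive over the planned tests.**
Assumed: each test is a t-test at two-sided 0.05, with no true effect and no drift.

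Two between-arm tests, if the outcomes are independent: 1 − 0.95² = 9.75%. Correlation between the sEMG and iEMG changes lowers this.

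For all four tests the independence formula does not apply, because the between-arm iEMG contrast is the difference of the two within-arm changes. The upper bound is the sum, 4 × 0.05 = 20%. A simulation that keeps the dependence (400,000 runs, 9 per arm) gives:

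| sEMG-iEMG correlation | two between-arm tests | all four tests |
|---|---|---|
| 0 | 9.8% | 16.0% |
| 0.5 | 9.1% | 15.2% |
| 0.9 | 7.1% | 13.1% |

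Results at 7 and 10 per arm are almost the same (7.1-9.8% and 13.2-16.1%). The documents give no correlation, so the range is the answer: about 7-10% for two tests and 13-16% for four.

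**Step 3. Within-arm comparisons under a common drift.**
Assumed: no treatment effect, 9 analysable per arm, a paired t-test at two-sided 0.05, and the same drift in both arms, in units of the SD of change. The documents give no drift figure. With p the chance that one arm is significant, and independent arms, the chance that capsaicin is significant and placebo is not is p × (1 − p):

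| drift (SD) | p | p × (1 − p) |
|---|---|---|
| 0 | 0.050 | 4.8% |
| 0.2 | 0.083 | 7.6% |
| 0.4 | 0.185 | 15.1% |
| 0.6 | 0.354 | 22.9% |
| 0.8 | 0.559 | 24.7% |
| 1.0 | 0.748 | 18.8% |
| 1.5 | 0.975 | 2.5% |

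The last row falls because both arms are then nearly always significant.

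**Step 4. Sample size under alternative remedies (sEMG variable only).**

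- One primary test at 0.05: 7 per group, 9 with dropout, as planned.
- Bonferroni over the two between-arm tests (0.025 each): 9 per group (power 84.4%; 8 gives 78.4%); 9 / 0.8 = 11.25, so 12 with dropout.

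No equivalent calculation is possible for iEMG variance, because the documents give no effect size or SD for it.

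**The case against.** **The stated error rate is met.** A reader might infer that the 5% in Section 3 is not delivered. The documents do not support that. Section 3 attaches 5% to one named variable, Section 2.4.1 tests that variable once, in one muscle, with one value per participant, and no family-wise 5% is promised. This part of the objection stands.

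**Recruitment change already has implicit priority.** Section 3 sizes on it alone, and Appendix A works through only that variable. This is true, but the Abstract and the hypothesis set both outcomes side by side, and an implied priority does not bind the report.

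**The inflation could be read as larger.** A reader might multiply out four independent tests. Three of the four share the same iEMG data, so that calculation overstates the risk; the simulated range is the one to use. A reader might also suppose that both outcomes must be significant and work out a joint power. The plan sets no such requirement and gives no iEMG effect size to base one on.

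**The drift figures rest on an assumed input.** This stands: the 15-25% applies only to drifts of about 0.4-1.0 SD and falls away on either side. They also assume a paired test that Section 2.4.2 does not name, since both tests it names compare independent groups. And they assume 9 analysable per arm, although Section 2.3.2 excludes participants without a match of at least 0.95. The logical point, that a pre-post change does not isolate treatment, needs none of these inputs.

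**This is a small mechanistic study with no stated decision rule.** The plan says only that the analyses give insight, and it already includes the valid between-arm iEMG comparison. For separately reported claims, formal adjustment is debatable. That argues for labelling over splitting the error rate. It does not remove the need to say which result is confirmatory, since the plan gives a formal power calculation and never calls its iEMG analyses exploratory.

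**Conclusion.** The concern holds as a missing hierarchy, together with within-arm comparisons offered as evidence. It does not hold as a failure of the Section 3 calculation, which is correct for its one variable.

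Over the planned set, the chance of at least one false positive is roughly 1.4 to 2 times the nominal 5% for the two between-arm tests and 2.6 to 3.2 times for all four. That is conditional on each test being run at 0.05 and on the range of correlations shown. The within-arm pattern of capsaicin significant and placebo not is unreliable evidence of an arm difference. How often it misleads depends on a drift that the documents do not quantify: from about 2.5% to 25% over the values examined. The point should be settled before analysis, and it does not call the design or the sample size into question.

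**What to change.** Amend Section 2.4 as follows:

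- Name the between-arm comparison of sEMG recruitment change (trapezius) as the single primary test, at two-sided 5%.
- Label the between-arm iEMG variance comparison either as secondary, tested only if the primary is significant, or as exploratory.
- Report the within-arm iEMG changes as estimates with 95% confidence intervals, and draw no treatment conclusion from them.
- Reword the sentence in 2.4.2 that links the analyses to the hypothesis so that it refers to the between-arm comparison only.

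The cost is wording alone: every planned measurement is kept, and the size stays at 7 per group, 9 with dropout. The downside is that an isolated iEMG result could no longer be claimed as confirmatory. If the sponsor wants both between-arm outcomes to be confirmatory in their own right, sharing the 5% equally would need 9 per group (12 with dropout) for the sEMG variable, and an effect size and SD would first have to be stated for iEMG variance.
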